### **3.6 Sampling and type of sampling**

Taking into account local statistics on the incidence of coagulated hemothorax of 16.7%, with the intention of reducing it to 5%, we need a sample of 125 patients in each arm, that is, approximately 250 patients in total, calculating a loss of patients of 15% in each arm. According to statistical data from the Pablo Tobon Uribe Hospital, in 2015, 148 patients underwent closed thoracostomy, for which a total patient collection time of approximately 20 months is calculated.

### **3.7 Bias control**

#### **3.7.1 Information bias:**

The data will be entered in the form intended as interventions are carried out on the patient

### 3.7.2 Diagnostic bias:

Chest x-ray read by surgeon and urgentologist on duty. A nomogram will be used to measure the amount of blood in the chest and define if it requires a closed thoracostomy

### 3.7.3 Randomization:

Randomization was made in EPIDAT4.0, defining the sequence of the intervention and non-intervention groups based on the consecutive admission of the patient to the study.

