### 2.2 Specific:

- Evidence other complications other than coagulated hemothorax, related to closed thoracostomy
- To determine the specific complications of the operated group in relation to aspiration under sedation of the pleural space
- Microbiological analysis of coagulated hemothorax in the population included in the study that presents this complication

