### 3 METHODOLOGY

#### 3.1 Type of study:

Prospective, randomized, controled

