#### 3.5 Exclusion criteria:

- Any previous surgical procedure in the hemithorax to intervene
- Hemodynamic instability requiring urgent thoracotomy in the patient
- Drawing blood from the chest cavity that defines massive hemothorax
- Outflow of intestinal / gastric material, bile, chyle or saliva from the hemithorax at the time of performing a closed thoracostomy
- Patient who entered the service with a closed thoracostomy performed

- Need for major surgical intervention in the injured hemithorax to perform repair of an intrathoracic injury.

- Contraindication for sedation and moderate analgesia in the emergency department: those patients at risk of complications such as craniofacial malformations, predictors of difficult airways, serious or decompensated heart disease, lung, liver, kidney or central nervous system diseases, morbid obesity, sleep apnea, pregnant women

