## **3.8 Collection of information**

A direct source consisting of the completion of a form by the professionals in charge of the patient is used, from the moment they enter the emergency department.

The patient and companions will be questioned about trauma situations and possible risk factors

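### Section 3.7.3 describes no allocation concealment and does not require eligibility to be fixed before the arm is revealed, so entry to each arm is open to selection

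*Combined protocol and SAP*

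**What the plan says.** The design is given in 3.1 as "Prospective, randomized, controled". Section 3.7.3 contains the whole allocation procedure: a sequence generated in EPIDAT 4.0, "defining the sequence of the intervention and non-intervention groups based on the consecutive admission of the patient to the study". The rest of 3.7, the section on bias control, deals with entering data on the form and reading the chest x-ray. No section mentions a list holder, envelopes, central release, the order of eligibility and assignment, or blinding.

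Three other places bear on this:

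- **3.5, exclusions needing judgement before the procedure.** One is "Contraindication for sedation and moderate analgesia in the emergency department", which the text expands into airway predictors, serious organ disease and similar items. Another is "Need for major surgical intervention in the injured hemithorax to perform repair of an intrathoracic injury".
- **3.5, exclusions that appear only once the chest is entered or drained.** These are blood loss that defines massive hemothorax, and escape of gut contents, bile, chyle or saliva "at the time of performing a closed thoracostomy". Their timing relative to assignment is not stated.
- **2.2 and 3.8.** One specific objective is "To determine the specific complications of the operated group in relation to aspiration under sedation of the pleural space", which ties sedation to the intervention. Data come from "completion of a form by the professionals in charge of the patient".

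**The concern.** Software generation makes a sequence random; it does not keep it hidden. If the person deciding whether a patient qualifies can learn the next assignment, a borderline exclusion can be applied more or less strictly depending on that assignment. The sedation criterion is the obvious place for this, because aspiration is the procedure the protocol links to sedation. The operator cannot be kept unaware of the arm once aspiration is assigned, so concealment up to entry is the main protection available against selective enrolment.

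What is at stake is the comparability of the arms. Patients who are held back never reach the database. Section 3.9 plans chi-square tests and bivariate comparison without adjustment, and no screening log is described, so an imbalance created at entry would be neither visible nor correctable.

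**Working it through.** **Plan's own figure.** Section 3.6 gives 16.7% versus 5%, 15% loss, and 125 per arm. Alpha and power are not stated; I assume two-sided 0.05 and 80%. With unpooled variance:

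n = (1.960 + 0.842)² × (0.167×0.833 + 0.05×0.95) / (0.167 − 0.05)² = 107 per arm

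107 / 0.85 = 126, against the stated 125, so the figure reproduces closely. Evaluable patients per arm after loss: 125 × 0.85 = 106. The point about concealment does not depend on this; it only sets the size used below.

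**Illustration of selective entry with no true effect.** From the documents: overall event rate 16.7%, and 106 per arm. Assumed: 30% of candidates are high-risk with event rate pH, and a fraction f of them is held back before aspiration slots only.

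- Low-risk rate, keeping 16.7% overall: pL = (0.167 − 0.30·pH) / 0.70
- High-risk share left in the aspiration arm: h = 0.30(1 − f) / [0.30(1 − f) + 0.70]. For f = 0.5, h = 0.15/0.85 = 0.176.
- Aspiration-arm rate: pA = h·pH + (1 − h)·pL. The control arm stays at 16.7%.
- Chance of a false significant benefit: the exact binomial probability, over all pairs of event counts, that the uncorrected two-sided 5% chi-square is significant in favour of aspiration.

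With no selection this chance is 2.5%. With f = 0.5:

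| High-risk rate pH | Low-risk rate pL | Aspiration-arm rate | Chance of false benefit |
|---|---|---|---|
| 20% | 15.3% | 16.1% | 3.3% |
| 25% | 13.1% | 15.2% | 4.8% |
| 30% | 11.0% | 14.4% | 6.9% |
| 35% | 8.9% | 13.5% | 9.7% |

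With f = 0.1 the chance is 2.6% to 3.2% over the same range. If high-risk patients are instead held back before control slots, the calculation is symmetric and the same figures become the chance of a false significant harm.

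**The case against.** The strongest reply is that silence is not evidence. A reader might infer that the list was open, or that assigning the nth place to the nth entrant makes the next arm knowable. Neither follows. Any sequential list works this way, including one in sealed numbered envelopes, so the rule is compatible with full concealment. That objection stands: foreknowledge is possible, not shown.

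Several narrower objections also stand.

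- **Sedation.** The exclusion in 3.5 applies to every candidate, and no section says control patients have the tube placed without sedation. An arm-specific motive is plausible but inferred.
- **Extent of judgement.** The airway and organ-disease items belong to the single sedation exclusion and should not be counted as separate criteria. The need for a tube is guided by a nomogram and a two-reader x-ray (3.7.2).
- **Direction.** A reader might infer that the bias would favour aspiration. Staff who believe in aspiration could equally steer worse cases towards it.
- **Size.** The documents do not link sedation risk to clotted hemothorax, so the gap between strata is undocumented; the 35% row assumes roughly a fourfold gap. Larger figures (11.4% and 30.1%, at 30% and 50% hold-back each way) appear if low-risk patients are also held back before control slots. The sedation mechanism gives no reason for that, so I do not rely on them.

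What the reply does not do is supply a safeguard. Staff following the protocol as written have no instruction to keep the list hidden or to fix eligibility first, and a reader cannot credit a procedure that is not specified.

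**Conclusion.** The point holds as a missing safeguard. The protocol provides no allocation concealment and no rule that eligibility precedes assignment, in a trial with judgement-based exclusions, one of which concerns sedation, under which the intervention is performed. It does not hold as a finding that allocation was open or that selection occurred.

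Its size cannot be derived from the documents. On the assumed inputs, the effect ranges from almost nothing at 10% hold-back to nearly four times the nominal 2.5% (9.7 / 2.5 = 3.9) at 50% hold-back with the widest risk gap. The stratum share, the high-risk rates, the hold-back fractions and the one-way pattern are all assumptions. The case for acting rests on the low cost of the remedy and on the bias being beyond repair at analysis, not on any single figure. I class it as a cheap improvement.

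**What to change.** Add a paragraph to 3.7.3 stating that:

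1. the EPIDAT list is held by existing staff who neither enrol nor treat these patients;
2. each assignment is released by sequentially numbered, opaque, sealed envelope, or an equivalent locked form;
3. release happens only after every 3.5 criterion that can be assessed before the procedure has been recorded with date and time;
4. a log is kept of all screened thoracostomy patients, with the reason for any non-entry;
5. any exclusion that becomes evident only at drainage is logged by arm, because envelopes do not prevent exclusions made after assignment.

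The sequence is described as already generated. If concealment of this kind was in use, stating how the list was held and released closes that part of the gap.

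Cost: about 250 envelopes, a log, one paragraph of text and roughly a minute at the bedside. No extra patients or staff are needed, and no clinical criterion changes.

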## **3.8 Collection of information**

A direct source consisting of the completion of a form by the professionals in charge of the patient is used, from the moment they enter the emergency department.

The patient and companions will be questioned about trauma situations and possible risk factors

## **3.9 Data analysis**

The form data will be entered in a database of the SPSS program. Analysis of each separate group will be performed and then a comparison based on days of hospitalization, percentage of hemothorax retained, empyema, need for surgery, postoperative pain, reoperation or readmission. Chi2 test to establish statistical significance of these differences, with a bivariate analysis
